#### **8.4.2 Analysis of the secondary efficacy outcomes - amended**

Analysis of the secondary efficacy outcomes will be based on the intention-to-treat principle (Section 8.2) and will use a similar approach as described in Section 8.4.1. The family-wise error rate will be controlled using the truncated and/or regular Hochberg tests as described in Section 8.4 and more detailed in the SAP.

#### **8.4.3 Analysis of the tertiary efficacy outcomes**

Analysis of the tertiary efficacy outcomes will be based on the intention-to-treat principle (Section 8.2) and will use a similar approach as described in Section 8.4.1 (except for SAGE, MoCA, DSS, and EQ5D). Analysis of subject reported SAGE, MoCA, DSS, and EQ5D will be described in the SAP. Both comparisons of the rivaroxaban-based treatment groups to the common aspirin control group will be performed at the 2-sided 5% type I error level. Additional exploratory analyses will be conducted, as described in the SAP.

The MRU data will be incorporated into economic modeling, which will be performed and reported separately from this study.

#### **8.4.4 Analysis of the primary safety outcome**

The principal analysis of the primary safety outcome will be based on the intention-to-treat principle (Section 8.2). The analysis will follow similar methodology as the analysis of the primary efficacy outcome described in Section 8.4.1.

In addition, the primary safety outcome will be analyzed based on the other data scopes defined in Section 8.2.2.

#### **8.4.5 Analysis of the outcome for pantoprazole randomization - amended**

Analysis of the outcome for pantoprazole randomization will be based on the intention-to-treat principle (Section 8.2) and will include all subjects randomized to receive pantoprazole 40 mg od or pantoprazole placebo.

Pantoprazole 40 mg od treatment group and pantoprazole placebo control group will be compared. The null hypothesis  $H_{0;panto40}$  stating that “there is no difference between the pantoprazole treatment and control groups in the probability of the outcome for pantoprazole randomization for all time points” will be tested against the alternative hypothesis  $H_{1;panto40}$  stating that “there is a difference between the two groups in the probability of the outcome for at least one time point”.

The comparison will be performed using a log-rank test stratified by antithrombotic therapy study group (3 strata levels: rivaroxaban 2.5 mg bid + aspirin 100 mg od; rivaroxaban 5 mg bid + aspirin placebo; rivaroxaban placebo + aspirin 100 mg od), conducted at the 2-sided 5% type I error level. There will be no interim analyses for the pantoprazole randomization.

Kaplan-Meier estimates of cumulative risk and cumulative hazard functions will be provided to evaluate the timing of event occurrence in the 2 PPI study groups and the consistency of the treatment effect for all time points (the 2 survival curves do not cross).

 Paragraph was revised as per Amendment 8. (See Section 13.2.2)

 Text deleted as per Amendment 6. (See Section 13.1.2)

Hazard ratio, relative risk reduction, and corresponding 2-sided 95% confidence intervals will be estimated based on a Cox proportional hazards model stratified by antithrombotic therapy study group. Censoring will be assumed independent of the treatment group assignment. Similar strategies to those outlined in Section 8.4.1 will be used for assessing the plausibility of the proportional hazards assumption.

In addition, joint effect and interaction between the antithrombotic and pantoprazole study groups will be explored based on the intention-to-treat principle in subjects randomized to receive pantoprazole 40 mg od or pantoprazole placebo. The analysis will use 2 separate Cox proportional hazards models, one for the comparison of rivaroxaban 2.5 mg bid + aspirin 100 mg od vs. rivaroxaban placebo + aspirin 100 mg od, and one for the comparison of rivaroxaban 5 mg bid + aspirin placebo vs. rivaroxaban placebo + aspirin 100 mg od. The models will include:

- a covariate for the effect of the considered rivaroxaban-based treatment group vs. the aspirin control group,
- a covariate for the effect of pantoprazole 40 mg od treatment group vs. pantoprazole placebo control group,
- an interaction term of these 2 factors.

If the interaction term is significant at the 5% type I error level, then the interaction ratio test (36) will be performed to assess synergy and sub-additivity of the two treatment effects. Additional exploratory analyses, e.g. a comparison of subjects who used PPI at baseline (and therefore were not randomized to receive pantoprazole 40 mg od or pantoprazole placebo) with subjects randomized to pantoprazole placebo group, will be conducted as described in the SAP.

#### **8.4.6 Subgroup analyses - amended**

Subgroup analyses for the primary efficacy and safety outcomes, and the outcome for pantoprazole randomization will be performed based on the same analysis sets and data scopes as in the main analyses of the study outcomes (Sections 8.4.1, 8.4.2, 8.4.3, 8.4.4, and 8.4.5).

Homogeneity of treatment effect in subgroups, both in magnitude and direction, will be assessed by adding a covariate for the subgroup variable (Section 8.3.6) and the corresponding treatment-subgroup interaction to the respective stratified Cox proportional hazards model used in the main analysis. Cox proportional hazards regression model (not stratified) will be used for baseline PPI use (yes, no) variable.

As the number of subgroup analyses may be large, the probability of observing at least one statistically significant but spurious interaction is high despite the lack of a biological or pharmacological basis for expecting an interaction. Thus any significant interactions in the analysis of primary outcomes will be interpreted as “flags” to prompt further investigation.

---

 Text deleted as per Amendment 6. (See Section 13.1.2)

No interactions with any of the subgroup variables are expected. If the interaction term is significant at the 5% type I error level in the analysis of the primary efficacy outcome, secondary and tertiary efficacy outcomes will be investigated to evaluate the plausibility of such an effect. Furthermore, in the analysis of all outcomes if the interaction term is significant at the 5% type I error level the likelihood ratio test proposed by Gail and Simon(37) will be performed to test the hypothesis that there is no crossover or qualitative interaction at the 1% type I error level ( $H_0$ : The direction of treatment effect is the same for all levels of a subgroup variable vs.  $H_1$ : The direction of treatment effect is different for at least one level of a subgroup variable). As was shown by Li et al (2007),(38) the probability of observing the treatment effect in the opposite direction to the true overall treatment effect for at least one subgroup level is not negligible. The contributing factors may be small subgroup sizes, imbalance of randomized groups within the subgroups, and small true overall treatment effect.(38)

Following the test of interaction, hazard ratio and relative risk reduction for the treatment effect will be estimated separately within each level of a subgroup variable using the stratified Cox proportional hazards models that were used in the main analyses of study outcomes.

#### **8.4.7 Handling of missing data**

All efforts will be made to collect complete data for all subjects randomized in this study. Subjects will be followed to the study end and will complete all required data collection, regardless of their compliance with study medications or visits.

When an event date is not known, the site investigator will be asked to provide a best estimate as to when the event occurred. Even though the exact date of an event is unknown, the investigator often does know some information that would indicate the approximate date, such as the first week of a month, in the fall of a year, or the middle of a particular year, or at least the date when the subject was last seen or contacted. This information can be meaningfully incorporated into the estimated date recorded, as this is likely to be closer to the true date than any produced by an uninformed computer program. This estimated date should be the middle date within the period that the event is known to have occurred. If the event is known to have occurred in the first week of a month, then the date in the middle of that week should be recorded as the estimate. If it occurred in the fall of a year, then the middle date in the fall is the appropriate estimate. If no information is known then the date in the middle of the plausible time period should be given, based on the last contact with the subject prior to the event and the date of contact when information about the event was known. This method for date estimation has been used in many studies and is recommended by Dubois and Hebert (2001).(39)

#### **8.4.8 Long-Term Open-Label Extension – amended**

All primary, secondary, tertiary efficacy outcomes and safety outcomes will be summarized using frequency table in a descriptive way. Further details will be included in a separate SAP. The same subgroup variables as in the COMPASS trial will apply to LTOLE.

---

 Text added as per Amendment 11. (See Section 13.3.1)

## 8.5 Planned interim analyses - amended

Interim assessments and study monitoring for efficacy and safety will be done by an independent DSMB, which will review unblinded event rates. An independent statistician within PPD, who is not involved with any study conduct, will perform interim data analyses to support the DSMB.

Two formal interim analyses are planned when 50% and 75% of the expected number of accumulated primary efficacy outcome events accrue.

If the interim analyses show clear and consistent benefit in both treatment arms, the DSMB may recommend early study termination. The Haybittle-Peto rule will be used to guide the decision regarding early stopping: a reduction of 4 standard deviations in the analysis of the primary efficacy outcome at the first interim analysis or 3 standard deviations at the second interim analysis. If the monitoring boundary is crossed at either of the 2 interim analyses, a second look will be done after at least 4-6 months to confirm the boundary remains crossed and that the trend in treatment effect is not temporary.

For a lack of efficacy, a futility approach will be utilized at the time of planned interim analysis. If the conditional probability of rejecting the null hypothesis for either primary comparisons, given current trends, falls to an unacceptably low level (i.e. <5%), the DSMB may consider recommending early termination of the study.

Given these conservative monitoring boundaries and only 2 interim analyses, the type I error level adjustment for the final analysis will be negligible. If the results are clear with one intervention, but not for the second intervention, the DSMB may decide to continue evaluation of both or one rivaroxaban treatment arms. If the study is continued with both interventions, then the type I error levels specified in Section 8.4.1 will be used in the final analysis; if the decision is made to continue with only one intervention, the final comparison will be made as follows: 

- If one intervention was stopped early for efficacy, the multiple testing procedure for the final analysis will be performed as described in Section 8.4 with the assumption that the p-value for the primary efficacy outcome of the arm that was stopped early for overwhelming efficacy is smaller than 0.025. For secondary outcomes, the p-values will be obtained from log-rank tests based on all available data for the stopped arm (data from confirmation analysis 6 months after respective interim look) and the complete data from the comparator arm.
- If one intervention was stopped early for futility, the final analysis will be performed when at least 1,513 subjects in the 2 remaining arms have experienced an event.

---

 The details in the bulleted paragraphs were added as per Amendment 8. (See Section 13.2.2)

 The whole study was planned to be stopped when at least 2,200 subjects had experienced a primary outcome event. Under the planning assumptions that both alternative hypotheses are true, observed randomization times and estimated overall incidence rates based on preliminary data, and projected study duration after sample size increase, it is expected that 826 subjects in the control arm and each 687 subjects in the rivaroxaban intervention arms will experience a primary outcome event. Dropping one intervention arm early but still expecting that for the other comparison the alternative hypothesis holds true, the study needs to be continued until at least  $826 + 687 = 1,513$  subjects in the remaining arms have experienced a primary event.

The final analysis will be performed according to the multiple testing strategy as described in Section 8.4. P-values for the primary and secondary hypotheses for the intervention stopped early will be obtained from the log-rank tests based on all available data for the stopped arm and the complete data from the comparator arm. It can be assumed that for the stopped intervention the corresponding p-value of the primary efficacy outcome will be greater than 0.05. Thus, for the intervention stopped early for futility the primary and none of the secondary outcomes can achieve statistical significance at the overall type I error level of 5%.

The Steering Committee will review overall blinded event rates to ensure that they meet protocol projections. If overall event rates are lower than expected, consideration will be given to increasing the sample size or extending the study duration without knowledge of any treatment effect. The trial will aim to enroll about one-quarter subjects with PAD; this will be monitored during the trial and steps may be taken to adjust the proportion during the trial.

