### Testing strategy

---

 Text deleted as per Amendment 6. (See Section 13.1.2)

 Bullet was added as per Amendment 8. (See Section 13.2.2)

Each of the rivaroxaban-based treatment groups will first be compared to the common aspirin control group on the primary efficacy outcome, followed by the same comparisons on the three ordered secondary efficacy outcomes. Figure 8–1 illustrates the hypothesis testing problem with ordered hypotheses. The null hypotheses of no effect corresponding to different efficacy outcomes will be grouped into four separate families. Standard logical restrictions will be imposed, i.e., the null hypotheses will be split into two branches corresponding to the tests for rivaroxaban 2.5 mg plus aspirin (hypotheses  $H_{1A}$ ,  $H_{2A}$ ,  $H_{3A}$ ,  $H_{4A}$ ) and to the tests for rivaroxaban 5.0 mg (hypotheses  $H_{1B}$ ,  $H_{2B}$ ,  $H_{3B}$ ,  $H_{4B}$ ). A null hypothesis within each branch can be tested if and only if the immediately preceding null hypothesis is rejected, e.g., hypothesis  $H_{2A}$ , is “testable” if and only if hypothesis  $H_{1A}$  is rejected. In Figure 8–1, these logical restrictions are represented by arrows.

[figure not shown]

Figure 8–1: Hypothesis testing problem

Multiple hypotheses testing will be performed according to a mixture gatekeeping procedure based on the Hochberg test with a truncation fraction of  $\gamma = 0.9$ , which controls the familywise error rate at the pre-assigned level of significance  $\alpha = 5\%$  in the strong sense. The Hochberg-based gatekeeping procedure based on an extension of the general mixture methodology developed in Dmitrienko and Tamhane (33,34) was recently proposed in Brechenmacher et al. (32) Details for the setting of this study will be described in the SAP.

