**Table 8–1. Events calculations**

| Assumed annual incidence rate in aspirin control group | Expected total study duration (years) | Estimated power for one comparison | Expected total number of events |
|--|---------------------------------------|------------------------------------|---------------------------------|
| 3.0%   | 4.5                                   | 85.1%                              | 1,642                           |
|  | 5.0                                   | 89.2%                              | 1,909                           |
| 3.5%   | 4.5                                   | 90.2%                              | 1,907                           |
|  | 5.0                                   | 93.4%                              | 2,215                           |
| 4.0%   | 4.5                                   | 93.7%                              | 2,171                           |
|  | 5.0                                   | 96.0%                              | 2,517                           |

Based on these estimates and the aim to detect a true relative risk reduction of 20% in each of the rivaroxaban arms with at least 90% power, it was planned to randomize at least 21,400 subjects and to continue the study until a minimum of 2,200 subjects experience an event for the primary efficacy outcome. In this multi-center study, each center is expected to randomize at least 50 subjects.

The originally planned sample size of 21,400 and 5 year study duration was based on an annual primary incidence rate in the control group of 3.5% and 90% power to detect a relative risk reduction of 20% in each of the rivaroxaban arms. Based on an observed incidence rate of 2.9% as of July 2015, it is now planned to randomize at least 27,400^151 subjects. This new sample size will maintain current study timelines and 90% power to detect a 20% relative risk reduction in each of the rivaroxaban arms, based on the following revisions to the original assumptions:

- Overall length of recruitment period about 3 to 3.5 years and taking observed randomization times up to July 2015 into account
- 2-sided overall type I error level of 5% using a truncated Hochberg test ( $\gamma = 0.9$ ) for the testing of the two primary hypotheses
- Constant overall incidence rate of about 2.9% per year, resulting in a constant incidence rate of about 3.3% per year for the aspirin control group assuming a 20% relative risk reduction for both hypotheses

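### After an early efficacy stop, secondary outcomes are tested with fixed-sample p-values and no sequential boundary, so strong familywise control is asserted for them but not guaranteed

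*Protocol*

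**What the plan says.** Section 8.4 (Testing strategy) uses "a mixture gatekeeping procedure based on the Hochberg test with a truncation fraction of" 0.9. Of this procedure the protocol asserts, in the strong sense and for a level of 5%: "which controls the familywise error rate at the pre-assigned level of significance". The order within an arm is strict: "A null hypothesis within each branch can be tested if and only if the immediately preceding null hypothesis is rejected".

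Section 8.5 schedules the looks: "Two formal interim analyses are planned when 50% and 75% of the expected number of accumulated primary efficacy outcome events accrue". The efficacy guide is the Haybittle-Peto rule, "a reduction of 4 standard deviations in the analysis of the primary efficacy outcome at the first interim analysis or 3 standard deviations", the smaller limit belonging to the 75% look. A crossing has to be confirmed at a later look, given as at least 4-6 months afterwards. The section then concludes that "the type I error level adjustment for the final analysis will be negligible".

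For one arm stopped early for efficacy, Section 8.5 takes its primary p-value as below 0.025 and runs the Section 8.4 procedure at the final analysis. "For secondary outcomes, the p-values will be obtained from log-rank tests based on all available data for the stopped arm", with the stopped arm's data cut at the confirmation analysis (here given as 6 months after the look) and complete data from the comparator. No boundary, spending function or reduced level is given for the secondaries. The section gives no rule for them if both arms stop.

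Section 8.6 reports simulations confirming that the procedure keeps the 5% level, and describes them as being for the primary efficacy outcome.

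**The concern.** A gatekeeping procedure controls the familywise error only if each p-value fed into it is valid for its own null hypothesis. Here the time at which a secondary is tested is chosen by the primary statistic. The secondaries share events with the primary, so the two statistics are positively correlated. A null secondary is then more likely to be tested early when it happens to be running high. The limits of 4 and 3 standard deviations protect the primary against this, but not the secondaries.

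Among the possible safeguards, the remark that the adjustment is negligible rests on boundaries that exist for the primary alone, and the simulations are described for the primary alone. The gap falls on the claims the procedure was brought in to support: Section 13.2.1 (Amendment 8, Modification 2) says it was adopted to allow a potential label claim on secondary outcomes. An arm stopped for futility is not affected, because Section 8.5 rules out significance for its secondaries.

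**Working it through.** **Inputs from the protocol.** Overall level 5%, two-sided, and gamma 0.9 (Sections 8.4, 8.6); looks at 50% and 75% of primary events with limits 4 and 3 (8.5); expected events 826 in control and 687 in each rivaroxaban arm (8.5, footnote); 27,400 subjects and overall incidence of 2.9% per year (8.6).

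**Assumptions, not in the protocol.** Primary-secondary correlation 0.5 to 0.95; the same information fractions for primary and secondary; stopping whenever the boundary is crossed and still crossed at confirmation; no extra information from comparator data collected after the cut.

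**Levels implied by the truncated Hochberg test.**
- Larger p-value: (0.9 + 0.1/2) x 0.05 = 0.0475.
- Smaller p-value: (0.9/2 + 0.1/2) x 0.05 = 0.025.
- Passed down if only one primary is rejected: 0.05 - 0.0475 = 0.0025.
- Passed down if both are rejected: the full 0.05, so a first secondary can be tested at up to 0.0475.
- Benefit-direction halves: 0.0475/2 = 2.375% and 0.0025/2 = 0.125%.

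**The plan's own figure.** Simulating two log-rank statistics against a shared control (correlation 0.5 from 1:1:1 allocation) under the global null gives a primary-family error of 4.76% at a fixed sample and 4.79% with the interim looks. The stated 5% limit is reproduced for the primary family, and the looks add almost nothing there.

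**Planned strength of the primary.** Events 826 + 687 = 1,513; hazard ratio 687/826 = 0.832; expected final Z = sqrt(1,513/4) x ln(826/687) = 19.45 x 0.184 = about 3.6.

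**Confirmation lag as information.** 27,400 x 0.029 / 2 = about 397 events in 6 months; 397/2,200 = about 0.18. The secondary of a stopped arm is then tested at about 0.50 + 0.18 = 0.68 or 0.75 + 0.18 = 0.93 of the information.

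**Error for a null secondary.** Paths were simulated over a range of constant primary effects. The table gives the largest benefit-direction error for one branch.

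| Nominal | Confirmation cut | Correlation 0.5 to 0.95 | Relative excess |
|---|---|---|---|
| 2.375% | +0.18 (about 6 months) | about 2.55-2.8% | about 7-18% |
| 2.375% | +0.09 (half that lag) | 2.59-2.92% | about 9-23% |
| 2.375% | no lag | 2.65-3.17% | about 11-34% |
| 0.125% | +0.18 | about 0.137-0.15% | about 10-20% |

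At the 2.375% level the maxima lie at an expected final Z of about 3.0 to 4.5, which includes the planned 3.6. In the full two-arm procedure with both first secondaries null, the benefit-direction error is 2.6-2.8% with the lag and 2.65-3.2% without it, against 2.5%.

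**Total two-sided error.** Under a constant effect it never exceeded 4.8%, because rejections in the wrong direction are mostly lost at the gate. If the primary effect may vary arbitrarily over time and the correlation is 1, the least-favourable two-sided error at level 0.0475 is 5.9% (75% look plus final), 7.0% (all looks, no lag) or 6.4% (with the lag).

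**The case against.** The strongest reply is that the protocol claims a two-sided 5% level ("2-sided overall type I error level of 5% using a truncated Hochberg test") and that this level was not exceeded under any constant effect. That stands. A reader might infer that familywise control fails in the planned scenario; the calculations do not show that.

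The confirmation step matters too. The secondaries are tested at the later cut, and the primary must still be beyond its limit there. A calculation that tests at the crossing look suggests an excess of up to about a third; under the rule as written it is roughly half that.

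A reader might also infer that the secondaries always receive the full level. They do not: if the other arm's primary is not rejected, only 0.0025 is passed down, and the absolute excess is then 0.01-0.03 percentage points.

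The upper end of each range needs a correlation near 0.95. That fits the two composites, which share most components with the primary, but a truly null effect on them beside an effective primary is hard to credit. All-cause mortality is a more plausible null, but it is tested last. Stopping is also at the data monitoring board's discretion, not automatic.

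Finally, details are deferred to the SAP, which is not shown and could add a boundary. That is only a partial answer, because Section 8.5 does more than leave the matter open: it states which p-values are used and gives no adjustment.

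**Conclusion.** The point holds in a limited form. As Section 8.5 is written, strong control for the secondary outcomes of an arm stopped early for efficacy is asserted but not guaranteed, and the reported simulations do not address it. The false-benefit error exceeds its nominal value by about 7-18% in relative terms (2.375% to about 2.55-2.8%) if confirmation comes about 6 months after the look, and reaches about 3.2% if there is no lag. These figures depend on the assumed correlation of 0.5 to 0.95 and on the conversion of 6 months into 0.18 of the information.

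The lag is itself not firmly fixed: Section 8.5 says at least 4-6 months in one place and 6 months in another, while Section 1.1 reports a crossing sustained over a 3-month period.

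Both rivaroxaban comparisons were stopped together in February 2017 (Sections 1.1 and 7.1), so the one-arm rule was not literally the one used. Section 8.5 states no rule for the secondaries in the case that did arise.

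**What to change.** In Section 8.5, state that each secondary hypothesis has its own group-sequential boundary, from a named spending function, applied to the level passed down by the gatekeeping procedure and evaluated at the information fraction of the confirmation cut. State that the same rule applies if both arms stop. Give one confirmation interval throughout.

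As an illustration, an O'Brien-Fleming-type boundary at level 0.0475 for tests at 50%, 75% and 100% of the information is Z = 2.89, 2.36 and 2.05 (two-sided p of 0.0038, 0.018 and 0.041); the values would be recomputed for the actual cut. It holds the benefit-direction error at or below 2.375% for any primary effect and any correlation. With correlation 1 and no lag, the simulated maximum falls from 3.5% to 1.5%. Extending the Section 8.6 simulations to the secondaries with interim stopping would document this.

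The change is to wording in the protocol and SAP, at the price of some power for secondary claims after an early stop. For the comparisons already stopped, a boundary chosen now would be post hoc and should be labelled as a sensitivity analysis.
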